2. SYNOPSIS

Using a novel locally grown health service delivery model in rural Bangladesh that tracks the universe of newly married couples and connects them to local health services, we aim to study whether targeting mothers early in pregnancy with three complementary interventions -- individually or in combination -- can improve their own wellbeing as well as their children’s developmental outcomes. The three interventions that we plan to pilot in a randomized controlled trial are: (1) information on the importance of early life conditions on future outcomes; (2) information and enrolment support to relevant government programs (including health services, cash- and food-transfers); and (3) psychological counselling. Our outcomes of interest include women’s empowerment, parental inputs, physical and mental health, and children’s health and development. Our partnership with the relevant government ministry in Bangladesh and an NGO offers a unique opportunity to implement evidence-based policy at scale.

TITLE	The Effect of Maternal Beliefs, Mental Health, and Economic Resources on Human Capital Accumulation in Early Life
OBJECTIVES	
 1) Explore what are pregnant women’s views about the idea of a “healthy pregnancy” and how these perceptions translate to health behaviours and investments in children. 2) Investigate if providing targeted interventions (health services, cash- and food-transfers, and psychological

	
counselling) to women early in pregnancy offer cost-effective ways to enhance children’s physical health, and maternal wellbeing and their physical and mental health.

PRIMARY HYPOTHESIS	
Our study has four main hypotheses, each of which will be tested by a different intervention:
 
1) According to government data, programs aimed for women with children are often undersubscribed, which may be largely explained by the fact that many poor women are not aware of the existence of these programs, their potential eligibility, or how to navigate the system to get enrolled. In fact, among the relatively few mothers that do get enrolled, they are often enrolled too late into (or even after) their pregnancy, missing critical windows for fetal development. Given this, we hypothesis that providing information on government programs and enrolment support will improve program take-up and women and children’s outcomes.2) While knowledge on the signature importance of the “fetal origins” and early childhood periods (Barker, 1990, Almond and Currie 2011) is widespread among clinicians and social scientists, the full range of effects may be less known to disadvantaged groups such as women in remote areas in low- and middle-income countries. Thus, to the extent that expectant mothers’ beliefs underestimate the returns of prenatal investments on children’s future outcomes, or misperceive the malleability of fetal health, we hypothesise that interventions that target maternal beliefs starting in early in pregnancy will be effective at promoting children’s future potentials.3) Research has shown that while psychological interventions conferred substantial benefit to mothers, they have not been effective in improving outcomes for children (Baranov et al. 2020, Angelucci and Bennett 2021). A likely cause is that interventions typically start too late (in the third trimester of pregnancy), and we hypothesis that a early start of psychological interventions will result in substantial benefits to mothers’ and children’s outcomes.

	
4) In low-income settings agents are often faced with numerous challenges that may interact in ways that prevent information or psychological interventions alone from generating significant or sustained improvements, and even more so to other agents within the household. Indeed, recent work suggests that poverty and low psychological well-being mutually reinforce each other in a vicious cycle (Ridley et al. 2020). We hypothesis that relaxing multiple constraints, namely through information provision, economic transfers (cash, food, services), and psychological counselling will be complementary, reinforcing each other (Haushofer et al. 2020, Angelucci and Bennett 2021).

DESIGN
	
This is a 3x2 factorial RCT of 2,640 participants across two sub-districts in rural Bangladesh. The two information interventions will be cross-randomized with the one mental health intervention.

BLINDING/MASKING
	
Participants will be able to know if they have been assigned to the treatment group as they will receive either information, services, counselling, or all three.

OUTCOMES
	
We will measure women’s empowerment, parental investment, mother’s physical and mental health, and child’s physical health and cognitive and socio-emotional development. We list the specific outcome variables below.
 
Maternal outcomes: Women’s empowerment (women’s agency in fertility planning, personal expenditures and expenditures on children, children and household investment decisions, savings accounts, and participation in social programs and local leaderships); Women’s beliefs (about importance of early life conditions, self-efficacy in parenting, beliefs about modifiability of child skills); Parental Investment (time, monetary, and warmth); Physical health (self-reported physical health, body-mass index, and mid-upper arm circumference (MUAC)); Mental health (PHQ-9 a screener for depression, GAD-7 a screener for anxiety); intimate partner violence (IPV); and Stress (Cohen Stress Scale, Biomarkers of stress using hair samples¹).

¹ We plan to collect biomarkers of stress from mothers and their infants. Using hair samples, we can extract HPA axis hormones such as cortisol. Hair-derived biomarker measurement indicates HPA axis activity over the course of months (analytes in each centimeter of hair approximate hormone secretion over one month), and thus more

	
Child outcomes: Health at birth (birth weight and low birth weight); Developmental outcomes (Bayley Scales of Infant and Toddler Development that captures children’s cognitive, language, motor, adaptive); Health (weight-for-length, length-for-age, acute respiratory illnesses); Stress (Biomarkers of stress from hair samples).

STUDY DURATION	
The estimated time (in months) from when the study opens to enrolment until completion of data analyses is 14 months.

INTERVENTION/S	
We will provide three interventions through the Kapasia Model of Maternal and Child Health (henceforth, Kapasia Model):
 
 1) Information about women’s eligibility to health services and other safety net programs (cash transfers, food transfers) offered by the government, and assist them with the enrolment process. 2) Information to pregnant mothers and their families on the importance of the early-life environment, and especially the 9-month in utero period, in laying the foundations for a child’s lifelong success. 3) Psychological counselling to pregnant women starting early in pregnancy.
NUMBER OF PARTICIPANTS	
A total of 2,640 women from 120 villages (22 women per village) from two sub-districts of Gazipur district will take part in this study. The information interventions will be randomized at the village level, with 40 villages receiving information and enrolment support for government programs, 40 villages receiving additional information on the importance of early life conditions, and 40 control (no information) villages. The psychological counselling intervention will be randomized at the Union Health and Family Welfare Centre (UHFWC) level (there are 20 total UHFWCs across the 2 subdistricts), stratified by sub-district, and allocated at a 1:1 ratio.

accurately reflect chronic hormone secretion (see Baranov et al. 2022 for a discussion and an example of successful hair cortisol measurement with mother and child dyads in Pakistan). Hair sample collection was funded with this proposal, and further funding will be sought for laboratory extraction of analysis. Hair samples are easily storable and stable for 1-2 years.


POPULATION
	
Our population includes newly married women, pregnant women, and mothers with young children aged 6 months or younger located in two subdistricts of Gazipur district in Bangladesh. According to the Demography and Health Surveys of 2014, women in Bangladesh tend to marry early. By age 18, 50% are married and their first child arrives 1.5 years later, which means that many women become mothers as teens. Moreover, 98.6% get married and nearly all have at least one child. As a result, there is virtually no selection into fertility in this setting. Two thirds of women deliver their child at home, have between one and two antenatal visits. Half have primary education or less, and less than 35% work outside home (half of which are employed in agriculture). Husbands are on average 10 years older, have similar levels of education, and the vast majority work in agriculture or in the informal sector. Moreover, Bangladesh has one of the highest rates of malnutrition in the world. 20% of children born in the country every year are born either “small” or “very small” (Demography and Health Survey, DHS 2014), 41% of those below the age of 5 are stunted, and about five million children are out of school (World Bank, 2015).

SELECTION AND ENROLMENT
	
Eligibility criteria for inclusion:
 
 1. Listed in the digital database of Kapasia Model 2. Permanent residence of any of the two subdistricts of Gazipur district in Bangladesh 3. Newly married women 4. Pregnant women 5. Mothers with young children aged 6 months or younger 
To be eligible, women must fulfill the first and the second criteria, any of the criteria from 3 to 5 must be fulfilled.

3. RATIONALE / BACKGROUND

In low- and middle-income countries (LMICs), over 250 million children under age five are not achieving their developmental potential due to adverse living environments (Black et al 2017). In Bangladesh, maternal and child deprivation is alarmingly high. The country has one of the highest rates of malnutrition in the world and about five million children are out of school (World Bank, 2015). Mothers in rural areas also face important economic and psychological challenges. During (and after) pregnancy, women experience a loss of status in the household

due to a reduced ability to supply labour. Further compounding stress from economic pressures, during this period women often experience an increase in Intimate Partner Violence (IPV) (Mojahed et al. (2021)). These factors combine to create an adverse intrauterine and early life environment that can have profound negative effects that propagate throughout the life course for the next generation (Almond and Currie 2011; Almond et al. 2018; Heckman 2016). While research has shown that well-designed interventions targeted at key developmental stages can help break the intergenerational cycle of disadvantage (Aizer and Currie 2014), most of this evidence comes from high- and middle-income settings. Yet there is an urgent need to understand whether and how welfare enhancing early-life interventions can be implemented at-scale and in cost effective ways in low-income countries.

We aim to investigate whether providing targeted interventions to women *early in pregnancy* offers cost-effective ways to enhance maternal wellbeing and children’s physical and mental development in rural Bangladesh. To do so, we will leverage a locally grown health service delivery model known as the *Kapasia Model*, that identifies hard-to-reach disadvantaged women as soon as they get married and tracks them on a digital database with the purpose of connecting them to health services and other safety net programs. The *Kapasia Model*, located in the sub-district of Kapasia, has been highlighted as a [best practice on maternal and child care](#) by the United Nations Population Fund and the Bangladesh Ministry of Health and Family Welfare has recently decided to scale it up.

Our project will be a collaborative effort with two ministries of Bangladesh, the Ministry of Health and Family Welfare (MHFW) and the Ministry of Women and Children Affairs (MWCA). The MHFW has already agreed to support our research, and we are in contact with the MWCA to collaborate on two of their *key* programs: the [Maternity Allowance Program](#) (targeting women in rural areas) and the [Lactating Mother Program](#) (targeting women in urban areas). Both programs provide unconditional cash transfers to pregnant and lactating women of Taka 800 (about \$25 in PPP) per month per woman for a duration of three years. These two welfare programs constitute the largest transfers of its kind for the MWCA. However, based on our discussions with key personnel within these Ministries these initiatives are often undersubscribed, which may be largely explained by the fact that many poor women are not aware of the existence of these programs, their potential eligibility, or how to navigate the system to get enrolled. In fact, among the relatively few mothers that do get enrolled, they are often enrolled too late into (or even after) their pregnancy, missing critical windows for fetal development.

We will introduce three interventions through the *Kapasia Model*. The first intervention would deliver information about women’s eligibility to health services and other safety net programs and assist them with the enrolment process. The second would deliver information to pregnant mothers and their families on the importance of the early-life environment, and especially the 9-month in utero period, in laying the foundations for a child’s lifelong success. While knowledge on the signature importance of the “fetal origins” and early childhood periods (Barker, 1990, Almond and Currie 2011) is widespread among clinicians and social scientists, the full range of effects may be less known to disadvantaged groups such as women in remote areas in LMICs. The third would introduce psychological counselling to pregnant women

starting *early* in pregnancy. Research has shown that while psychological interventions conferred substantial benefit to mothers, they have not been effective in improving outcomes for children (Baranov et al. 2020, Angelucci and Bennett 2021). A leading explanation is that interventions typically start too late (in the third trimester of pregnancy). The psychological counselling will be provided by our local collaborator, *Moner Bondhu* (“Friend of your mind”, <https://www.monerbondhu.org/>) – a local organization that provides care for mental health and well-being services. The organization has been very successful in reaching out to a large populace and has received numerous accolades from national and international organizations. We will investigate the role of maternal beliefs about the idea of a “healthy pregnancy” and its relationship with their children’s future health and economic outcomes. We will survey a sample of pregnant mothers to learn about their perceptions regarding the returns of different health-related behaviours in utero on their child’s outcomes in adulthood. To the extent that expectant mothers’ beliefs underestimate the returns of prenatal investments on children’s future outcomes, or misperceive the malleability of fetal health, the results of this paper could suggest that interventions that target maternal beliefs starting in early in pregnancy may be effective at promoting children’s potential.

This proposal contributes to the growing literature on the “psychological poverty trap.” We ask the question: is providing women with information more likely to lead to action when psychological constraints (like depression) and income constraints are relaxed? Research has shown that interventions aimed at reducing depression, like psychotherapy (Baranov et al. 2020, Vlassopoulos et al. 2021), can improve both mental health and economic decision-making. However, in low-income settings agents are often faced with numerous challenges that may interact in ways that prevent information or psychological interventions alone from generating significant or sustained improvements, and even more so to other agents within the household. Indeed, recent work suggests that poverty and low psychological well-being mutually reinforce each other in a vicious cycle (Ridley et al. 2020). Relaxing multiple constraints *simultaneously* may be necessary to break that cycle. Our study will test whether information provision, economic (cash, food, services) transfers, and psychological interventions are complements, contributing to an emerging literature testing how psychological support interacts with other, more traditional anti-poverty interventions (Haushofer et al. 2020, Angelucci and Bennett 2021).

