4. AIMS / OBJECTIVES / HYPOTHESES

Our goal is to address three types of adversities that hinder women’s empowerment and early child development in low- and middle-income countries: low take-up of healthcare and other social safety net programs (including cash- and food-transfers), lack of knowledge about the importance of the early years on future child development and long-run outcomes, and psychological constraints associated with maternal depression. We aim to test to what extent these three interventions offer practical opportunities to improve maternal health, birth, and child development outcomes in cost-effective ways. We believe that these interventions might be even more effective than previous similar interventions because we will be targeting women

early in pregnancy (and in some cases even prior to conception), which is considerably earlier than most previous studies aimed at improving maternal and child outcomes.

Our specific **objectives** are:

- 1) Explore what are pregnant women’s views about the idea of a “healthy pregnancy” and how these perceptions translate to actual health behaviours and investments in children.
- 2) Investigate if providing the three following targeted interventions to women early in pregnancy offers cost-effective ways to enhance maternal wellbeing and children’s physical and mental development:
 - a. Information about women’s eligibility to health services and other safety net programs and assist them with the enrolment process.
 - b. Information to pregnant mothers and their families on the importance of the early-life environment, and especially the 9-month in utero period, in laying the foundations for a child’s lifelong success.
 - c. Psychological counselling to pregnant women starting early in pregnancy.

Our study has four main **hypotheses**, each of which will be tested by a different intervention:

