- 1) According to government data, programs aimed for women with children are often undersubscribed, which may be largely explained by the fact that many poor women are not aware of the existence of these programs, their potential eligibility, or how to navigate the system to get enrolled. In fact, among the relatively few mothers that do get enrolled, they are often enrolled too late into (or even after) their pregnancy, missing critical windows for fetal development. Given this, we hypothesize that providing information on government programs and enrolment support will improve program take-up and women and children’s outcomes.
- 2) While knowledge on the signature importance of the “fetal origins” and early childhood periods (Barker, 1990, Almond and Currie 2011) is widespread among clinicians and social scientists, the full range of effects may be less known to disadvantaged groups such as women in remote areas in low- and middle-income countries. Thus, to the extent that expectant mothers’ beliefs underestimate the returns of prenatal investments on children’s future outcomes, or misperceive the malleability of fetal health, we hypothesize that interventions that target maternal beliefs starting in early in pregnancy will be effective at promoting children’s future potentials.
- 3) Research has shown that while psychological interventions conferred substantial benefit to mothers, they have not been effective in improving outcomes for children (Baranov et al. 2020, Angelucci and Bennett 2021). A likely cause is that interventions typically start too late (in the third trimester of pregnancy), and we hypothesize that a early start of psychological interventions will result in substantial benefits to mothers’ and children’s outcomes.
- 4) In low-income settings agents are often faced with numerous challenges that may interact in ways that prevent information or psychological interventions alone from generating significant or sustained improvements, and even more so to other agents within the household. Indeed, recent work suggests that poverty and low psychological

well-being mutually reinforce each other in a vicious cycle (Ridley et al. 2020). We hypothesize that relaxing multiple constraints, namely through information provision, economic transfers (cash, food, services), and psychological counselling will be complementary, reinforcing each other (Haushofer et al. 2020, Angelucci and Bennett 2021)

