6. RESEARCH PLAN / STUDY DESIGN

Our study is comprised of three treatments. In treatment 1, project officers employed by the research team, who will be located in study area, will provide information over the phone to each treated household on their eligibility (yes or no) of government's cash and food transfer programs, as well as where and how to enrol, and assistance with enrolment for eligible mothers.

Treatment 2 involves providing information to pregnant mothers and their families on the importance of the early-life environment, and especially the 9-month in utero period, in laying the foundations for a child's lifelong success. Eligible and willing participants who would be randomly assigned to receive this treatment will be contacted by our project officers, and the officer will provide the following information over the phone:

“A healthy pregnancy, wherein mothers take care of themselves and their children during their pregnancy, is extremely important for their children health and economic outcomes. Starting from as early as the 9th week of pregnancy, mothers who eat nutritious food and think positively give birth to healthier children who grow up to be healthier adults. A healthy diet during pregnancy such as this one, (this is based on study conducted in a similar setting, see: <https://bmjopen.bmj.com/content/bmjopen/7/8/e015393.full.pdf>)

Meal	Food	Quantity (one dish=250mL)
Breakfast	Rice	1.5 dishes
	or	
	Chapati (medium size)	3 pieces
	Vegetables	1 dish
	Egg	1
Mid-morning snack	Lentil (thick)	1 dish
	or	
Lunch	Seasonal fruit(s)	1 piece/dish
	Milk product(s)	1 dish
Afternoon snack	Rice	3 dishes
	Lentil (thick)	1 dish
	Leafy/non-leafy vegetables	1.5 dishes
	Meat/fish/egg	1 piece
Dinner	Milk	1 glass
	Seasonal fruit(s)	1 piece/dish
	Puffed rice with molasses or Biscuits	1 dish
Dinner	Rice	2 dishes
	Lentil (thick)	1 dish
	Leafy/non-leafy vegetables	1.5 dishes
	Meat/fish/egg	1 piece
	Milk or Curd	1 glass / 0.5 dish

	উপাদান	পরিমাণ
সকালের নাস্তা	ভাত	১½ বাটি (২৫০ মি.লি.+১২৫ মি.লি.)
	অথবা	অথবা
	অটার কুটি	৩টি (মাঝারি)
	সবজি ভাজি	১ বাটি (২৫০ মি.লি.)
	ডিম ভাজি	১টি
মাঝারি নাস্তা (সকাল ১০-১১)	যে কোন মৌসুমি ফল (মেম্বন-কলা/আম/কঁচালা/পেয়ারা/পেঁপে ইত্যাদি)	১টি (মাঝারি)
	অথবা	অথবা
দুপুরের খাবার	ভাত	৩ বাটি (২৫০ মি.লি.+২৫০ মি.লি.+২৫০ মি.লি.)
	মন ডাল	১ বাটি (২৫০ মি.লি.)
	শাক-সবজি	১ বাটি (২৫০ মি.লি.)
	মাছ/মাংস/ডিম	১ টুকরা (মাঝারি)
বিকালের নাস্তা	মুগ	১ গ্রাস
	অথবা	অথবা
সন্ধ্যার খাবার	দুধের তৈরী পায়েস/ফিরনি/পিঠা	½ বাটি (১২৫ মি.লি.)

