To evaluate the impact of these three interventions, we will conduct a 3x2 factorial RCT across two sub-districts in rural Bangladesh. The two information treatments will be cross randomized with the one mental health intervention. The mental health intervention will be randomized at the Union Health and Family Welfare Centre (UHFWC) level (there are 20 total UHFWCs across the 2 Upazilas), stratified by sub-district, and allocated at a 1:1 ratio. We will then randomly select 120 villages within subdistricts, stratified by UHFWC, to participate. The information interventions will be randomized at the village level, stratified by UHFWC, with 40 villages receiving information and enrolment support for government programs, 40 villages receiving additional information on the importance of early life conditions, and 40 control (no information) villages. Eligible participants will be pregnant women and mothers with young children aged 6 months or younger. We will aim to recruit 22 women per village to be part of the study sample.

We will use two types of data, (i) the data from the digital information system of Kapsasia Model built at the sub-district level by the local government, which we call *administrative data*, and (ii) household and individual survey data including elicitation of maternal beliefs of prospective and existing mothers that we will collect as a part of the study, which we call *household survey data*. This survey will be conducted on the sample of 22 women per village for a **total sample of 2,640 women**. The administrative data include information (e.g., age, education, occupation, mobile phone number, pregnancy status, birth outcomes, number of children) on *all* registered newly married couples in our study area, including the 22 women per village in our study sample, and will identify key outcomes such as pregnancy status and birth outcomes. We will conduct a baseline survey with an endline 10 months later, and we plan to conduct a midline survey by phone (which will likely be funded using internal funds² from the University of Sydney and University of Melbourne) to measure parental inputs in the in utero period. The schedule of enrolment, intervention and evaluations is given in Figure 1.

² They have not been mentioned in the budget as no firm commitment has been received yet.

The study schedule	Study period													
	Baseline							Midline				Endline		

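### Hypothesis 4 claims a complementarity test for economic transfers, but no cell assigns a transfer: the six cells identify two intention-to-treat interactions with counselling, and early-life information × enrolment support is not estimable

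*Protocol*

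**What the plan says.** The claim appears three times in the Protocol. The background (section 3) says "Our study will test whether information provision, economic (cash, food, services) transfers, and psychological interventions are complements". Hypothesis 4 in the synopsis (section 2) reads "We hypothesis that relaxing multiple constraints, namely through information provision, economic transfers (cash, food, services), and psychological counselling will be complementary", and section 4 repeats it: "namely through information provision, economic transfers (cash, food, services), and psychological counselling will be complementary". The background also asks: "is providing women with information more likely to lead to action when psychological constraints (like depression) and income constraints are relaxed". In each statement of the claim, transfers stand beside information as a separate component. Synopsis objective 2 likewise lists cash and food transfers among the interventions to be provided.

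The intervention itself is described differently. The opening of the synopsis has "information and enrolment support to relevant government programs (including health services, cash- and food-transfers". Objective 2a in section 4 is to inform women about their "eligibility to health services and other safety net programs and assist them with the enrolment process". In section 6, Treatment 1 is delivered by project officers who "will provide information over the phone to each treated household on their eligibility (yes or no", together with guidance on where and how to enrol and help in doing so. The cash comes from existing government programmes, and the background says the team is still only in contact with the ministry that runs the two named cash programmes.

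Section 6 sets the village allocation: 40 villages with enrolment support, then "40 villages receiving additional information on the importance of early life conditions, and 40 control (no information) villages". Figure 1 lists the second information arm as the first plus the early-life message. Counselling is crossed with these arms. Figure 1 schedules participation in transfer and safety-net programmes as an endline measure.

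**The concern.** A reader of hypothesis 4 would take transfers to be a randomised component whose interaction with information and counselling is tested. They are not. Whether a woman receives cash or food depends on her eligibility, on whether she takes up the offer and on government processing, all after allocation. Hypothesis 1 itself treats take-up as an outcome.

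What is at stake is what the trial may conclude. A positive interaction of the enrolment arm with counselling could come from the information that the arm delivers rather than from any transfer. A null one could come from low receipt. Under the present wording, either could be read as a finding about cash and food transfers. Separately, the wording promises complementarity between information and transfers. For early-life information, the allocation lacks a cell needed to examine this even at the level of enrolment support.

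**Working it through.** The question is one of identification, so the check is on the cells and the design matrix. The Protocol gives no figure for the complementarity test. Its minimum detectable effects (0.31 SD for counselling, 0.19 SD for either information arm) are stated for the counselling comparison and for information main effects, and do not bear on what is identified.

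**Inputs (Protocol sections 2 and 6, Figure 1).** Three village arms of 40 villages, 22 women per village, crossed with counselling yes or no. Let E = enrolment support, L = early-life information, C = counselling.

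- Women per village arm: 40 × 22 = 880.
- Total: 120 × 22 = 2,640, which agrees with the Protocol.
- Enrolment support assigned: 80 × 22 = 1,760 women, in 4 of 6 cells.
- Early-life information without enrolment support: 0 cells.
- Transfer assigned: 0 cells, 0 women.

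**Design as written.** (E,L) takes the values 00, 10 and 11, each with C = 0 and C = 1, giving 6 cells. The saturated model has 8 terms: 1, E, L, C, EL, EC, LC, ELC. Early-life information occurs only where E = 1, so columns L and EL are identical, as are LC and ELC. The rank is 6 of 8.

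- Separately estimable: 1, E, C, EC.
- Estimable only as sums: L + EL and LC + ELC.
- Not estimable: EL and ELC.

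**In cell means** μ(E,L,C):

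- Enrolment support × counselling, first information arm against control: [μ(1,0,1) − μ(1,0,0)] − [μ(0,0,1) − μ(0,0,0)] = EC. All four cells exist.
- Early-life information on top of enrolment support × counselling, second arm against first: [μ(1,1,1) − μ(1,1,0)] − [μ(1,0,1) − μ(1,0,0)] = LC + ELC. All four cells exist.
- Early-life information × enrolment support, without counselling: [μ(1,1,0) − μ(1,0,0)] − [μ(0,1,0) − μ(0,0,0)] = EL. The cell μ(0,1,0) does not exist.

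Each of the two identified contrasts uses 80 villages, that is 1,760 women.

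**Alternative reading of the second arm.** If it gave early-life information alone, (E,L) would be 00, 10 and 01. Columns EL and ELC would be zero throughout and the rank would again be 6. L and LC would then be estimable, but EL would still not be, because μ(1,1,0) would be missing.

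**Check against a full factorial.** With all 2 × 2 × 2 = 8 cells the rank is 8 and every term, including EL, is estimable. The loss comes from the missing cells, and no choice of analysis can recover it.

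**The case against.** The strongest reply is that economic transfers is shorthand for the arm that facilitates them. The synopsis opening, objective 2a, the Treatment 1 description and Figure 1 all describe that arm as information plus enrolment support. Hypothesis 1 names take-up as the pathway, and section 6 claims only that the information arms are crossed with counselling. This stands to the extent that the design section misleads nobody. It does not rescue hypothesis 4, which lists transfers beside information as separate components. Even with the shorthand accepted, the interaction of early-life information with enrolment support remains unestimable.

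A second reply is that naming the interaction estimand, or using assignment as an instrument for receipt, belongs in an analysis plan. Details of that kind may. The hypothesis and the arms are protocol content, however, and an analysis plan cannot supply a contrast that was never allocated. An instrumental analysis would need the arm to act only through receipt. That is doubtful for an arm that also informs, and the Protocol does not propose such an analysis.

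A reader might also infer more than the document supports:

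- *That enrolment support × counselling is the only identified interaction.* It is the only one bearing on the transfer programmes, but early-life information × counselling is also identified, given enrolment support. That contrast answers part of the background's question on psychological constraints.
- *That links to health services confound a transfer effect.* The Protocol's own label for transfers includes services, so only the information in the arm is a rival explanation.
- *That the primary outcomes already cover receipt of transfers.* The item on social programmes there is listed under women's empowerment. The clear source is the endline measure in Figure 1.

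**Conclusion.** The claim is wrong as written, and it is a main hypothesis. No cell assigns a transfer. The design supports two intention-to-treat complementarity contrasts: enrolment support × counselling, and early-life information added to enrolment support × counselling. It does not support a test of early-life information × enrolment support, and it gives the effect of early-life information only in the presence of enrolment support. The early-life × enrolment result holds under either reading of the second arm and needs no assumption about effect sizes, variances or clustering. The conditional reading of the early-life effect rests on the nested arms shown in Figure 1.

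No size can be put on the gap between enrolment support and receipt, because the Protocol gives no expected take-up. Nor does this make the trial invalid or its allocation faulty: the randomised comparisons stand, and the fault lies in what hypothesis 4 says they show.

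**What to change.** Change the wording in hypothesis 4 (synopsis and section 4), in the background, and in synopsis objective 2:

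1. Replace the reference to economic transfers with *information and enrolment support for government transfer and service programmes*.
2. State the two identified interactions separately, without pooling the two information arms: enrolment support × counselling (first arm against control), and early-life information added to enrolment support × counselling (second arm against first).
3. State that complementarity between early-life information and enrolment or income support is not tested.
4. Attribute no effect to receipt of transfers unless the added assumption, that the arm acts only through receipt, is stated alongside.

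These are edits to a few sentences, with no change to allocation, sample size or data collection. The price is a narrower claim than one about economic transfers. Keeping the information × enrolment claim would instead need cells with early-life information and no enrolment support, which is a design change and is not needed for the correction.
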